8.6 IRB/IEC Notification of SAEs and Other Unanticipated Problems

The Investigator will promptly notify the IRB of all on-site unanticipated, serious adverse events that are related to the research activity. Other unanticipated problems related to the research involving risk to subjects or others will also be reported promptly. Written reports will be filed using the eIRB system and in accordance with the timeline below. External SAEs that are both unexpected and related to the study intervention will be reported promptly after the investigator receives the report. External events that do not change the risk to subjects or result in a change to the research protocol will be reported to the IRB following IRB recommendations.

REPORTING REQUIREMENTS TO THE IRB		
Type of Unanticipated Problem	Initial Notification (Phone, Email, Fax)	Written Report
Internal (on-site) SAEs Death or Life Threatening	24 hours	Within 2 calendar days
Internal (on-site) SAEs All other SAEs	7 days	Within 7 business days
Unanticipated Problems Related to Research	7 days	Within 7 business days
All other AEs	N/A	Brief Summary of important AEs may be reported at time of continuing review

8.6.1 Follow-up report

If an SAE has not resolved at the time of the initial report and new information arises that changes the investigator's assessment of the event, a follow-up report including all relevant new or reassessed information (e.g., concomitant medication, medical history) should be submitted to the IRB. The investigator is responsible for ensuring that all SAE are followed until either resolved or stable.

8.7 Investigator Reporting Requirements to IRB and FDA

INVESTIGATOR REPORTING TO THE FDA/DEVICE MANUFACTURER			
Type of Report	Description of Report	Submit to:	Timeline
Unanticipated Adverse Device Effects	Report of any unanticipated adverse device effect	IRB and FDA	Within 10 working days after investigator first learns of effect.
Withdrawal of IRB approval	If IRB withdrawn from study site	Sponsor	Within 5 working days
Progress Report	FDA Form 3419	IRB, FDA, Sponsor	Regular intervals, no less than every 6 months for the first 24 months of the study. Then regular intervals, no less than yearly, after the first 24 months of the study.
Deviations from the investigational plan	If deviation of investigational plan occurred in order to protect subject's life or physical well-being (i.e. during an emergency)	IRB, Sponsor	Within 5 working days
Informed Consent	If investigator used device without obtaining informed consent	IRB, Sponsor	Within 5 working days
Final Report	Complete and final investigative report	IRB, Sponsor	Within 3 months of study completion or study termination
Other Reports	Any access or reports on request	IRB, FDA	Per request

Voluntary Reports	At discretion of investigator. Voluntary adverse event reporting is done through Form 3500A.	IRB, FDA	As deemed by investigator
--------------------------	---	----------	---------------------------

8.8 Sponsor Reporting Requirements to FDA and IRB

SPONSOR REPORTING TO THE IRB/FDA			
Type of Report	Description of Report	Submit to:	Timeline
Unanticipated Adverse Device Effects	Report of any unanticipated adverse device effect	FDA and reviewing IRB(s)	Within 10 working days after sponsor first receives notice. May submit further reports at FDA requests
Withdrawal of IRB approval	If IRB withdraws approval of investigation or part of the investigation	FDA and reviewing IRB(s) and participating investigators	Within 5 working days of receipt of notice
Withdrawal of FDA approval	If FDA withdraws approval	Reviewing IRB(s) and participating investigators	Within 5 working days of receipt of notice
Current Investigator List	Current list of names and addresses of all participating investigators	FDA	12 month intervals
Progress Report	FDA Form 3419	FDA and reviewing IRB(s)	Regular intervals, no less than every 6 months for the first 24 months of the study. Then regular intervals, no less than yearly, after the first 24 months of the study.
Recall and Device Disposition	If Sponsor requests return, repair, or disposal of device, and why	FDA and reviewing IRB(s)	Within 30 working days after request is made

Final Report	Complete and final investigative report	FDA and reviewing IRB(s)	
 1. Notify FDA within 30 working days 2. Submit final report to FDA and IRBs within 6 months
Informed Consent	If investigator used device without obtaining informed consent	FDA	Within 5 working days of receipt of notice
Significant risk device determination	IRB determination of significant risk of the medical device	FDA	Within 5 working days of receipt of notice of the determination
Other	Any access or reports on request	FDA and reviewing IRB(s)	Per request

8.9 Medical Emergencies

If a medical emergency occurs in the hospital system, it will be reported following the above guidelines and timelines. If no emergencies are identified through chart review, subjects will be asked at designated follow-up if they have sought medical care for any reason between research visits. Any events will be reported through the above policies and procedures.

Subjects who contact the study team or clinical offices regarding a medical emergency will be referred to the appropriate health care professional to manage their emergency, and contact will be documented in the medical record.

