3.1.3 Post-operative Follow-up

The post-operative follow-up phase of the study will last approximately 90 days, beginning with the day after the surgical intervention. This period has three set time points for follow-up, which will occur during standard-of-care clinical follow-up visits for spine patients receiving surgical intervention. The three time-points are a POD 21 wound check, POD-45 clinical visit, and a POD-90 clinical visit. During these three clinical visits physical exams, radiographs, and AE/SAE data will be collected depending on the visit. POD 2-44 will be monitored for known complications and AE/SAEs only, as there will be no clinical outcomes data to collect during this time. This data will be abstracted from the medical records. In addition, the patient will be under SOC post-operative care for patients who have undergone anterior spinal surgery. Data from any SOC interventions will also be abstracted from the medical record.

In unique circumstances, the Investigator may determine it is necessary for the Subject to be seen for a follow-up visit(s) at an outside institution due to geographic, travel, other restrictions. In such a case the Investigator will communicate with the physician evaluating the Subject at the outside institution and Subject to ensure all necessary data points and AE/SAE information are captured. If possible copies of the Subject's medical record for this visit will be obtained by the study team.

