4.4.3 Visit 8 (POD 730)

- X-ray: AP/PA and lateral spine
- X-ray: Bending bolster films (completed at treating physician's discretion)
- Pulmonary function test (completed at treating physician's discretion)
- History and physical exam with height and weight
- Research specific physical exam (research)
- Medical record review and abstraction (research)
- X-ray review and abstraction (research)
- Complications review (research)
- Clinical photographs (research)
- SRS 30 Questionnaire (research)
- Study completion CRF (research)

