8.5 Recording plan for AEs/SAEs

Surgery and Post-operative Phase (Day 0 – POD 90):

For these phases, all AEs (including SAEs) will be noted in the study records and reported per IRB and FDA requirements outlined below. The subjects will be encouraged to contact the office with any concerns, and the medical record will be monitored by study staff for indications of AEs.

Extended Follow-up Phase (POD 91-POD 730):

For this phase, all SAEs will be recorded (regardless of cause). Only AEs which are deemed “device related” will be recorded on study documents and reported per IRB and FDA requirements outlined below. The subjects will still be encouraged to contact the office with any concerns, and the medical record will be monitored by study staff for indications of SAEs or device-related AEs.

Long-term Follow-Up (POD 730 through approximately two years after skeletal maturity):

An observational study involving chart review of medical charts from CHOP and external sources as needed will be undertaken for long-term follow-up. All SAEs identified from the medical records that are considered device related, up to two years after skeletal maturity, will be reported in accordance with FDA requirements. This will be performed under a separate research protocol.

Only the AEs/SAEs indicated above will be recorded in a patient-specific study binder, kept in the secure orthopedics research office. The binder will contain a full description of the event, including the nature, date and time of onset, determination of non-serious versus serious, intensity (mild, moderate, severe), duration, causality, and outcome of the event. Hard copies of the primary documents (medical record notes) describing the event and any associated treatment will be printed and kept in the patient-specific study binder. A redundant copy of adverse events will be kept in the study REDCap database and will be maintained by the study team separately from the patient-specific study binder. The study binder will serve as the official record of all Events.

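### Section 8.9 asks families about care sought between visits only when chart review shows no emergency, so outside SAEs in children with a chart emergency may be missed

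*Combined protocol and SAP*

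**What the plan says.** Section 8.9 (Medical Emergencies) takes two steps. For events inside the institution: "If a medical emergency occurs in the hospital system, it will be reported following the above guidelines and timelines". Then: "If no emergencies are identified through chart review, subjects will be asked at designated follow-up if they have sought medical care". The question covers care for any reason between research visits, but is put only when the chart search is negative.

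Other sections also bear on event capture:

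- Section 8.5, day of surgery to POD 90: "The subjects will be encouraged to contact the office with any concerns, and the medical record will be monitored by study staff" for signs of AEs. For POD 91 to 730: "The subjects will still be encouraged to contact the office with any concerns". In that second period all SAEs are to be recorded whatever their cause, but only device-related non-serious AEs.
- Section 3.1.3: AE/SAE data are collected at the POD 21, 45 and 90 visits, without saying how. For monitoring over POD 2 to 44: "This data will be abstracted from the medical records". If a study visit is held at another institution, the investigator contacts the physician there.
- Sections 4.3.1 to 4.4.3: history and physical and a complications review at each of Visits 3 to 8.
- Section 4.6: at unscheduled visits, research procedures are limited to record abstraction and complications review.
- Section 3.3.1: off-study visits are captured only if related to an AE or SAE.

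**The concern.** The condition does not fit the purpose of the question. Chart review covers the hospital's own records; the question exists to find what those records do not show. A positive finding in the chart is no evidence that nothing happened elsewhere, yet as worded it removes the prompt that would reveal it. Section 3.1.3 itself foresees families who cannot easily travel to the site, so care elsewhere is a realistic prospect.

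Safety is the primary endpoint (section 6.1), defined as the rate of AEs/SAEs. Section 6.3.2 adds the number and type of events, frequencies by type, body system, severity and relationship, and device-related incidence with exact 95% intervals. Section 6.6.1 halts enrolment on counts of patients with a procedure-related SAE. Section 9.1 sends data to the manufacturer for a humanitarian device exemption submission. Missed events can only lower these counts.

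**Working it through.** The plan states no figure on this point, so there is nothing to reproduce. The check sets the sections side by side and then gives a scale under stated assumptions.

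**Step 1. Is there an unconditional question elsewhere?** Sections 3.1.3, 3.3.1, 4.3 to 4.6, 5.1.3 to 5.1.5, 5.2 and 8.5 contain none. History and physical and complications review apply to every child, but their content is not described. Section 5.1.3 lists the POD 21 evaluations as record review plus height, weight and BMI. Contact with the office under 8.5 depends on the family taking the initiative. External records, as needed, are named only for the separate long-term follow-up study.

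**Step 2. What switches the question off?** An emergency identified through chart review. An ordinary AE in the chart does not. The text does not say whether the check is made once or afresh for each interval between visits; since the question concerns care between research visits, a per-interval reading is natural.

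**Step 3. Which measures could change?** Suppose one outside SAE in a child with a chart emergency is missed:

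| Chart emergency | Missed outside event | Event count | Per-subject rate and stopping count in that category |
|---|---|---|---|
| Procedure-related SAE | Second procedure-related SAE | -1 | 0 |
| Unrelated event | Procedure-related SAE | -1 | -1 |
| Not device-related | Device-related SAE | -1 | -1 |

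Section 6.1 does not say whether its rate is per subject or per event; section 6.3.2 uses both a dichotomous AE variable and counts. Where the child does not already count, one subject moves a category incidence from 4/40 = 10.0% (exact 95% CI 2.8% to 23.7%) to 3/40 = 7.5% (1.6% to 20.4%), and could turn 7 of the first 10 patients, a halt under 6.6.1, into 6.

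**Step 4. How many children?** All inputs are assumptions except N = 40, the maximum enrolment. Let p be the share with a chart emergency at any time in the two years, and q = 15% the share with an SAE treated elsewhere, independent of p.

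- Reading A, one emergency suppresses the question for all of follow-up: N x p x q.
- Reading B, it suppresses the question for that interval only. With six intervals (surgery to Visit 3, then to each of Visits 4 to 8) and equal risk in each, the per-interval share is 1 - (1 - p)^(1/6), and the expected number is N x that share x q.

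| p | Reading A | Per-interval share | Reading B |
|---|---|---|---|
| 20% | 40 x 0.20 x 0.15 = 1.2 | 0.0365 | 40 x 0.0365 x 0.15 = 0.22 |
| 40% | 40 x 0.40 x 0.15 = 2.4 | 0.0816 | 40 x 0.0816 x 0.15 = 0.49 |
| 60% | 40 x 0.60 x 0.15 = 3.6 | 0.1416 | 40 x 0.1416 x 0.15 = 0.85 |

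These are children with an outside SAE who are not asked. They are a ceiling on children missed, because other routes will catch some.

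A second parameterisation gives missed events directly: let q be the share of children with a chart emergency who also have an outside SAE that only direct questioning would find. Under Reading A, 40 x 0.05 x 0.10 = 0.2 and 40 x 0.50 x 0.25 = 5 mark the ends of a wide range.

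**The case against.** A reader might infer that a child with any chart event is never asked, that outside SAEs in such children are therefore lost, and that the SAE rate and stopping counts are biased low in the sickest children. The documents do not support that.

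- The trigger is an emergency, not any event, and the wording allows a per-interval reading: an emergency before POD 45 need not suppress the question at POD 90 or later.
- History and physical, complications review, encouraged self-report and the all-SAE recording rule apply whatever the chart shows. That the content of the complications review is unstated does not prove families are not asked.
- Weaker ascertainment in complicated cases is not established. Section 8.6.1 requires SAEs to be followed until resolved or stable, and section 5.1.2.3 keeps complication status updated, so these children may have more contact with the team.
- The device-related stopping rules in 6.6.2 turn on re-operation, and spine films are scheduled at POD 45, 90, 180, 365 and 730. An implant re-operation elsewhere is unlikely to stay unseen.
- A child who already counts in a category adds nothing more to a yes/no rate or a per-patient limit.

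All of this stands, and it narrows the point. It does not remove it: the one explicit prompt about outside care is withheld for a reason unrelated to whether such care occurred, and none of the other routes is stated to ask about it.

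**Conclusion.** The gap in section 8.9 is real. Read literally, a child with an emergency in the hospital chart is not asked about care elsewhere, at least for that interval, and an SAE treated elsewhere may then be missed. The exposed quantities are event counts and types, and the procedure-related or device-related categories in which the chart emergency itself does not count; for device re-operations the scheduled films give partial protection. The direction can only be towards under-counting.

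The size is unknown, because the documents give neither the frequency of chart emergencies nor that of outside SAEs. With q = 15% and p from 20% to 60%, the ceiling is 0.22 to 0.85 children of 40 on the per-interval reading and 1.2 to 3.6 on the whole-follow-up reading. Both rest on assumed inputs, on independence and, for the per-interval figures, on equal risk across intervals. This is a defect in ascertainment that is cheap to remove, not evidence that the safety results would be materially wrong.

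**What to change.** Reword section 8.9 so that at every scheduled follow-up visit all subjects or families are asked whether they have sought medical care anywhere since the last contact, regardless of what chart review found. Record the answer on the CRF, including a negative answer, and request outside records when it is positive.

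Section 4.6 limits research procedures at unscheduled visits, so there the question should be written in as part of the complications review, which that section already allows. Defining the content of the complications review once, with this question in it, would serve both kinds of visit.

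The cost is one CRF item at visits that already take place, a few more record requests, and possibly a slightly higher recorded AE/SAE count. No clinical management changes.

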9 STUDY ADMINISTRATION

9.1 Data Collection and Management

1. Confidentiality:

A master list will be maintained separately from the coded data collection sheet and will contain the subject ID number, name, MRN, date of birth, dates of service, approximate date at which the subject will need to reconsent upon turning 18, and whether or not the subject has consented for the use of their data for future research studies. The list will be password-protected so that only the study staff will have access. Data will be collected on each subject using the subject's Study ID number. Data, including PHI, will be managed and stored using the research-focused electronic data capture system REDCap, under an agreement with the software's development consortium, led by Vanderbilt University. REDCap supports two secure, web-based applications designed exclusively to support data capture for research studies. REDCap is a PHP web application served by Apache Tomcat over a 128-bit SSL connection using a signed certificate. The application relies on a study-specific data dictionary defined in an iterative self-documenting process that will be conducted by all members of the research team. The data dictionary is the foundation for custom case report form design and validated coding of variables. Authentication of research staff will be performed via LDAP using CHOP's enterprise Active Directory service. The application generates a complete audit trail of user activity, provides reporting, and has an automated export mechanism to common statistical packages (SAS, SPSS, Stata, R/S-Plus).

A patient-specific study binder will be kept for each enrolled patient. The study binder will contain adverse event information, signed consent forms, paper forms collected during testing, as well as all other relevant documentation. These will be stored in a locked research office.

2. Data Sharing:

Coded data will be transferred from CHOP to [name] at Drexel University for research collaboration and data analysis via CD/DVD, secure electronic file transfer, and/or on protected Excel spreadsheets sent by secured hospital email. All data transferred will be labeled with the subject's study ID and will not include PHI. [name] at Drexel University will not have access to the master list, therefore this data will not be identifiable to them.

A Limited Data Set, including images, will be transferred from CHOP to Globus Medical, Inc. as part of a license agreement executed between the two parties for use in the manufacturer's humanitarian device exemption (HDE) submission. Images will be limited to images of subjects' torsos and will not include video recordings, subject faces, or identifiable features. Data will be sent by secure electronic file transfer and with hardcopy source documents. Hardcopy documents will be redacted to remove identifiers and be transferred via courier or in-person from study team member to an authorized representative of Globus Medical, Inc. Data transferred will

not include PHI, except dates of service, and Globus Medical, Inc. will not have access to the master list to link data back to subjects.

3. Security:

The master sheet will be a password protected Excel file kept in the secure orthopedic research drive at CHOP. The REDCap MySQL database is replicated in real time to a completely redundant instance of MySQL. The redundant instance is available for restoration of the primary database or for manual failover in the case of primary database failure. Time-stamped backup files are made from the replicated database daily by CHOP Research Information Systems using automated backup routines. Backup files are encrypted and transferred to a secure file server accessible only to designated personnel. A rolling seven-day window of backup files is maintained in an immediately available online state, with a larger window maintained in a compressed file archive available at a reduced speed of access. Daily destructive database backup files are stored on the database server and are deleted only after successful backup of the entire database to file. In the event of data error, loss or corruption, research personnel will work with CHOP Research Information Systems to determine the most appropriate recovery strategy. Data and backups are stored in the CHOP Research Information Systems Storage Area Network (SAN). Access to the SAN directories where data are stored will be limited to Research Information Systems personnel, with authentication performed using CHOP's enterprise Active Directory service. The data from the application will be compiled on a secured survey web platform that is encrypted using AES 256 bit encryption. The data collected on paper forms during testing will be secured in the patient-specific study binders in a locked research office.

4. Anonymization, de-identification or destruction:

Data will be collected on each subject using the subject's study ID number. Study personnel will store a list connecting the subject's PHI to study ID. All PHI collected from this study will be destroyed two years after the last marketing application has been approved or two years after all research of the study has been completed, and as approved by the Sponsor.

9.2 Confidentiality

All data and records generated during this study will be kept confidential in accordance with Institutional policies and HIPAA on subject privacy and that the Investigator and other site personnel will not use such data and records for any purpose other than conducting the study.

No identifiable data will be used for a future study without first obtaining IRB approval.

